7.1.6. Summaries of Adverse Events and Deaths

A brief summary of AEs will show, by monitoring group, the number and percentage of subjects who (1) had any treatment-emergent AE, (2) had any Grade 3 or 4 treatment-emergent AE, (3) had any Grade 2, 3 or 4 treatment-emergent AE, (4) had any treatment-emergent treatment-related AE, (5) had any Grade 3 or 4 treatment-emergent treatment-related AE, (6) had any Grade 2, 3 or 4 treatment-emergent treatment-related AE, (7) had any treatment-emergent SAE, (8) had any treatment-emergent treatment-related SAE, (9) permanently discontinued from TDF due to an AE, and (10) died during study.

Summaries (number and percentage of subjects) of adverse events (by SOC and PT) will be provided by monitoring group using the safety analysis set as follows:

- All treatment-emergent bone or renal AEs
- All TDF-related treatment-emergent bone or renal AEs
- Combined Grade 3 and 4 treatment-emergent bone or renal AEs
- Combined Grade 2, 3 and 4 treatment-emergent bone or renal AEs
- Combined Grade 3 and 4 treatment-emergent treatment-related bone or renal AEs
- Combined Grade 2, 3 and 4 treatment-emergent treatment-related bone or renal AEs
- All treatment-emergent serious AEs
- All treatment-emergent treatment-related SAEs

- All treatment-emergent AEs that caused permanent discontinuation from TDF
- All treatment-emergent AEs that caused change in dose or temporary interruption of TDF
- Deaths
- All AEs recorded between screening and first dose of TDF

For final analyses, summaries will be provided by monitoring group and overall TDF.

Summaries and data listings will use the Safety Analysis Set.

Events will be summarized based on the date of onset for the event, according to the definition of treatment emergent in Section 7.1.5. Non-treatment emergent events, including those prior to the first dose date of TDF, will be included in data listings.

Multiple events will be counted once only per subject in each summary. For data presentation, SOC will be ordered alphabetically, with PT sorted by decreasing total frequency. For summaries by severity grade, the most severe event will be selected.

In addition to the by-monitoring group summaries, data listings will be provided for the following:

- All AEs (with a variable indicating whether the event is treatment-emergent)
- SAEs (including deaths)
- AEs leading to discontinuation of TDF
- Subjects experiencing pregnancy during the study

PPD

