300mg oral Tenofovir disoproxil fumarate (Tenofovir DF), which is equivalent to 245mg Tenofovir disoproxil, following enhanced patient monitoring protocol for bone and renal biomarkers

Reference Therapy,
Dose, and Mode of
Administration:

300mg oral Tenofovir DF following local standards of care for patient monitoring for renal biomarkers

Criteria for Evaluation:

Safety:

The primary safety endpoint is the indication of a cumulative incidence of a $\geq 4\%$ decrease from Baseline BMD of the spine or whole body through Week 96. Secondary endpoints include bone and renal AEs. Bone AEs may include reports of bone pain or fractures. Renal AEs may include reductions in creatinine clearance, and clinical and laboratory evidence of Grade 3 or greater renal tubulopathy or toxicity (e.g. proximal renal tubulopathy, Fanconi syndrome).

Bone and renal AEs, concomitant medications (including dietary supplements) and specified clinical laboratory tests will be collected each time subjects from Group 1 or Group 2 return for scheduled monitoring by the study site over a 96 week period.

Efficacy:

An efficacy analysis will be conducted after the last assigned subject reaches Week 96. The analysis will evaluate the difference in the proportion of subjects (Group 1 and 2 data will be pooled, as subjects have exposure to a single mode of therapy) achieving a composite endpoint of HBV DNA < 400 copies/mL and ALT normal at Week 96.

Pharmacokinetics: Not applicable

Statistical Methods:

The primary safety analysis will be performed after the last subject reaches Week 96 on Tenofovir DF treatment among both monitoring groups. The primary analysis will evaluate quantitative reductions in spine or whole body BMD compared to baseline assessments through DEXA scanning. A key secondary study objective is to assess within-group and between-group differences in renal biomarker changes (e.g., creatinine clearance using the Schwartz formula, glucosuria, proteinuria) suggestive of renal toxicity. To evaluate the time to detection of renal or bone AEs among the assigned monitoring groups, estimations of incidence rates (events over person time on Tenofovir DF) and time to event analysis will be determined. The evaluation of other clinically relevant endpoints such as sustained virologic response, serologic status, and development of Tenofovir DF resistance will also be assessed as secondary study outcomes for each monitoring group and as a combined cohort.

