8.1.3. Secondary Endpoints

- Documentation of renal or bone AEs and outcomes among subjects receiving Tenofovir DF, including rates of medication withdrawal or drug discontinuation
- Subjects' cumulative exposure time on Tenofovir DF at the time renal or bone AEs are detected up to and including Week 96 or to study discontinuation (subjects without renal or bone AEs will contribute cumulative exposure time on Tenofovir DF from Baseline to Week 96 or to study discontinuation). The cumulative time to renal or bone AEs will be expressed as incident rates.
- Documentation of the medical management and classification of detected renal or bone laboratory abnormalities
- Analysis of subjects' virological and immunological status from Baseline to Week 96 under real world treatment practices
- Report provider recommendations and subject adherence to dietary supplements (e.g., Vitamin D, calcium)
- Documentation of subject demographics, new medical issues, medications, biometrics, treatment adherence
- Reasons for discontinuation of Tenofovir DF

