1.1. Study Objectives

Primary Study Objectives
	
To characterize the long term (i.e., 96 weeks of follow up) bone safety profile of open-label TDF treatment in adolescents with CHB. This includes prospectively evaluating and comparing the bone mineral density (BMD) changes between CHB- infected adolescents 12 to < 18 years of age treated with TDF in European treatment centers who were assigned to one of two schedules for renal and bone laboratory monitoring and BMD measurements. Primary study endpoint was the percent changes in BMD from Baseline through study Week 96.

Secondary Study Objectives
	
 • To document all serious adverse drug reactions (SADR) and all renal- and bone-related adverse events (AEs), including renal and bone laboratory abnormalities • To determine the time to diagnosis of renal and bone AEs and document the resulting patient management and outcome(s) • To assess the clinical management and outcomes of renal- and bone-related \geq Grade 3 laboratory parameters and clinical SAEs. • To assess the efficacy and tolerability of TDF in adolescents with CHB infection • To assess the use of oral vitamin D, calcium and phosphate supplementation and explore the association between supplement use and rates of bone and renal AEs • To describe the demographics and disease characteristics of adolescents with CHB infection treated with TDF.

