1.4. Sample Size and Power

Planned Sample Size	100 subjects (50 subjects to one of two monitoring groups)
Power Statement	
The study employed two monitoring protocols which specified the same laboratory and imaging tests for bone and renal markers and differed in the frequency of testing. Group 1 receives more frequent monitoring which is protocol-defined or SmPC specified, and Group 2 subjects are monitored according to a less frequent DXA schedule for BMD and followed the local standard of care for renal monitoring. It is hypothesized (H_0) that there would have been no difference in the timing, management, or subject outcomes resulting from renal or bone AEs among the two monitoring regimens. With a one-tailed test of $\alpha=0.05$, and assuming a non-inferiority margin of 0.10, the study had at least 80% power to detect a difference between the monitoring regimens beyond the specified margin of non-inferiority.
 
The primary safety endpoint is cumulative incidence of at least a 4% decrease from study baseline (BL) in spine bone mineral density (BMD) through Week 96.
 
The null hypothesis is the difference (Group 1 – Group 2) is equal to 0.
 
The alternative hypothesis is the difference (Group 1 – Group 2) is not equal to 0.

Actual Enrollment and Impact on Power	
The study failed to achieve its targeted enrollment of 100 patients, 50 per monitoring group. The study was discontinued as a result of the recent approval of Tenofovir alafenamide fumarate (TAF) medicine which offers a safer treatment option for CHB patients and due to low subject enrollment after the CHMPs assessment of the 18 month interim enrollment report. At the time of its closure the study enrolled 30 patients, 15 per monitoring group. The total enrolled subjects are underpowered to statistically detect differences in outcomes between monitoring groups.

--	--

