2. TYPE OF PLANNED ANALYSIS

2.1. Final Analysis

Final Analysis includes the time period from the first date of OL TDF dose through and including the date of last OL TDF dose plus 30 days. As a result of early study termination (FPFV July 2015 to LPLV April 2018) only two patients completed 96 weeks of observation on TDF treatment for HBV, the primary study objective to characterize the safety profile (renal and bone adverse outcomes) of subjects will be summarized based on available TDF exposure time. The assessment of efficacy and tolerability of TDF will be described. As most of the enrolled subjects were unable to complete the target observation period of 96 weeks, the final analysis will be unable to provide meaningful evidence to suggest whether enhanced or standard of care renal and bone monitoring frequencies between Group 1 and Group 2 offer early detection and mitigation of renal or bone adverse events. Instead, the data will be described by monitoring group and pooled together where possible.

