7.8. Changes From Protocol-Specified Safety Analyses

No alterations to the protocol-specified safety analysis have been made. The study has been canceled due to low enrolment and due to the approval of TAF for HBV in adolescents in November 2016 as a safer treatment option for patients. With two subjects completing 96 weeks of treatment the safety analysis will shift to focus on subjects' available treatment exposure to TDF.

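### Only 2 of 30 subjects reached Week 96, yet the readable SAP gives renal and bone AE occurrence as counts and percents, without the protocol's person-time rates or time to diagnosis

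*SAP*

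**What the plan says.** **Protocol.** The Synopsis (Statistical Methods) states that, for renal or bone AEs, "estimations of incidence rates (events over person time on Tenofovir DF) and time to event analysis will be determined". Sections 3.1 and 8.1.3 make exposure time at AE detection a secondary endpoint, with event-free subjects contributing time until Week 96 or discontinuation: "The cumulative time to renal or bone AEs will be expressed as incident rates". Section 8.6 plans cumulative incidence by time-to-event methods. Section 8.6.2 separately plans AE tables of counts and percents.

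**SAP, aims and circumstances.** Section 1.1 keeps the objective "To determine the time to diagnosis of renal and bone AEs". Section 1.4 reports: "At the time of its closure the study enrolled 30 patients, 15 per monitoring group". Section 2.1 reports that "only two patients completed 96 weeks of observation on TDF treatment for HBV". Sections 2.1 and 7.8 say that safety will be described on the exposure actually accrued, but name no estimator.

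**SAP, outputs.** Section 7.1.6 reads: "Summaries (number and percentage of subjects) of adverse events (by SOC and PT) will be provided by monitoring group using the safety analysis set". Tables 19.1 to 20 in Appendix 3 cover AE occurrence, management and outcomes, and supplement use. None is titled as a rate, person-time or time-to-diagnosis table. Exposure is summarised on its own (4.3.1, Table 6). Section 7.8 opens with "No alterations to the protocol-specified safety analysis have been made" and then describes a shift of focus to available exposure.

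**The concern.** A percent of subjects with an event mixes two things: how often events occur and how long subjects were watched. With complete 96-week follow-up it estimates the 96-week risk. Here follow-up was cut short for 28 of 30 subjects and must differ between subjects, since two completed and "most of the enrolled subjects were unable to complete the target observation period of 96 weeks". The percent then refers to no defined period and sits below the risk over the period the study was set up to describe.

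The SAP gives up the comparison of groups, so a description of renal and bone risk on TDF is a main product left. The protocol's exposure-based endpoint suits that situation, and it is the one with no readable output. The retained time-to-diagnosis objective likewise has no derived result.

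**Working it through.** **1. The plan's own figure.** Protocol 8.9 expects 4 to 5 renal or bone drug reactions in 100 subjects over 96 weeks. Its renal rate of 4.5% gives 100 × 0.045 = 4.5, which reproduces it. The BMD-loss rate of 5.8% would give 5.8. I therefore use 4.5% as the illustrative 96-week risk.

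**2. Inputs.**
- From the SAP: 30 enrolled (1.4) and 2 who completed 96 weeks (2.1), so 30 − 2 = 28 truncated.
- Assumed: all 30 were dosed; overall mean exposure *m* is 24 to 72 weeks (the documents give none); the hazard is constant; the 28 share one exposure *w*.

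**3. Formulas**, with 52.18 weeks per year.
- Hazard: h = −ln(1 − 0.045) / (96/52.18) = 0.0460/1.840 = 0.0250 per year, or 2.50 per 100 person-years.
- Exposure of the 28: w = (30m − 2 × 96)/28.
- Person-years: PY = 30m/52.18.
- Expected crude percent: [2 × 0.045 + 28 × (1 − exp(−h·w/52.18))]/30.
- Zero events: Poisson upper 95% limit = 3.689/PY; carried to 96 weeks, 1 − exp(−1.840 × 3.689/PY).

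For m = 48: w = (1440 − 192)/28 = 44.6 weeks and PY = 27.6. The expected percent is [0.090 + 28 × 0.0212]/30 = 2.27%, which is 51% of 4.5%.

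| Mean weeks | PY | Expected crude % | Share of 96-week risk | Expected subjects with event | One event: rate per 100 PY | One event: 96-week risk | Zero events: upper limit at 96 weeks |
|---|---|---|---|---|---|---|---|
| 24 | 13.8 | 1.14 | 25% | 0.34 | 7.25 | 12.5% | 38.9% |
| 36 | 20.7 | 1.71 | 38% | 0.51 | 4.83 | 8.5% | 28.0% |
| 48 | 27.6 | 2.27 | 51% | 0.68 | 3.62 | 6.4% | 21.8% |
| 60 | 34.5 | 2.84 | 63% | 0.85 | 2.90 | 5.2% | 17.9% |
| 72 | 41.4 | 3.39 | 75% | 1.02 | 2.42 | 4.3% | 15.1% |
| 96 | 55.2 | 4.50 | 100% | 1.35 | 1.81 | 3.3% | 11.6% |

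**4. Reading the table.** One event in 30 is 3.3% crude whatever the exposure, but corresponds to a 96-week risk of 4.3% to 12.5% over the assumed range. For zero events in 30, the exact binomial upper limit is 1 − 0.025^(1/30) = 11.6%. It equals the Poisson-based limit at full follow-up, so the rise to 15.1%–38.9% comes entirely from missing exposure. With 5.8% in place of 4.5%, the share captured is 25% to 76%, so it hardly depends on the planning rate.

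**The case against.** **Redaction.** SAP 7.1.7, headed as additional AE analysis, is blacked out, as is the end of 7.1.6. Appendix 3 cannot settle the matter because it is not exhaustive. Its numbering skips from 19.2.1 to 19.2.3; the any-grade bone or renal tables promised in 7.1.6 are not listed; nor are the summaries promised for prior HBV medication (7.5) and body weight (7.4). This stands: one cannot say that the SAP contains no rate, only that the readable text and table list show none.

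**The quoted sentence follows the protocol.** Protocol 8.6.2 itself asks for counts and percents. This stands: nothing is wrong with 7.1.6 as far as it goes. The gap is against the Synopsis and Protocol 3.1, 8.1.3 and 8.6.

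**Other outputs exist.** Tables 19.6 to 19.8, Listings 12 and 15.1, and cumulative incidence of BMD loss by week (SAP 7.3, Tables 26.1 and 27.1) are planned. With about one event or fewer expected, a listing carries much of the information. This limits the point to AE occurrence. It does not supply a rate or time to diagnosis, and the contents of Listing 15.1 are not specified.

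**Stronger readings.** A reader might infer that the percents will be presented as 96-week risks. The documents do not support that: the AE tables carry no Week 96 label, and SAP 2.1 discloses the early stop. A reader might also infer that the group comparison is biased. Exposure by group is not given, allocation was 1:1, and SAP 2.1 disclaims meaningful evidence on that comparison. Nor is the change hidden: 7.8 describes the shift, and its fault is that it contradicts itself.

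**Assumptions.** Exposure and hazard shape are assumed. Protocol 1.4 reports early BMD loss that then stabilises in HIV-infected adults and says no such pattern is established in children. If risk falls early, crude percents lose less and extrapolation to 96 weeks overstates. A Poisson rate does not remove this. SAP 7.1.6 specifies no confidence interval, so the limits above are illustrations, not planned outputs.

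**Conclusion.** The point holds in limited form. A protocol secondary endpoint, incidence rates over person-time for renal and bone AEs, and a retained objective, time to diagnosis, have no readable output in the SAP. Section 7.8 both denies and describes a change. The sections that might contain the missing analysis are redacted.

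Because 28 of 30 subjects did not complete 96 weeks, crude percents describe risk during truncated, unequal exposure and would understate the 96-week risk. As an illustration, about 25% to 75% of it is captured for mean exposures of 24 to 72 weeks. The size rests on the assumed exposure and constant hazard. The direction needs only that some risk remains after subjects leave observation.

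This should be changed, because truncated follow-up makes the protocol's exposure-based endpoint more useful. Small numbers justify dropping tests, but not a descriptive rate.

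**What to change.** Unless redacted 7.1.7 already does so:

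- In SAP 7.1.6 and Appendix 3, keep the counts and percents. Beside them report events, person-years on TDF, and the rate per 100 person-years with exact Poisson 95% interval for bone, renal and serious AEs, for Group 1, Group 2 and pooled. State how events in the 30 days after last dose are handled, so that numerator and denominator cover the same period.
- Add a listing of weeks from first dose to diagnosis for each renal or bone AE.
- Label the crude percents as occurring during available exposure.
- Correct 7.8 to list the departures from the protocol's time-to-event and person-time analyses.

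No new data are needed. First and last dose dates already define exposure (SAP 4.3.1), and onset dates define treatment emergence (7.1.5.1). The cost is a few columns, one listing and revised wording. The intervals will be wide and less favourable, and the output stays descriptive.
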